6.8 Secondary Analysis

There will be both safety and efficacy assessments in the secondary analysis.

The secondary safety analysis will consist of identifying the following:

- Percent of patients with ≥ 5 mmHg increase from baseline in IOP at each visit
- “Abnormal” and “Severe” slit-lamp biomicroscopy findings at the Baseline, Day 1, and Day 7 Visits
- Contact lens protein deposits at the Day 7 Visit
- Change from Baseline in CLDEQ-8 results at the Day 7 Visit

The secondary efficacy analysis will consist of identifying the change from baseline in IOP at each visit. Study eyes only within the modified intent-to-treat population will be used for this part of the analysis.

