**Day 1 (Visit 6): Lens insertion**

- Concomitant medications
- AEs
- Heart rate and blood pressure - *procedure should be performed before study intervention*
- BCVA - *procedure should be performed before study intervention*
- Biomicroscopy - *procedure should be performed before study intervention*

- IOP (measured at 8 am  $\pm$ 1 hour) - *procedure should be performed before study intervention*
- LL-BMT1 insertion of new lens
- Contact lens assessment
- LL-BMT1 removal (directly before 4 pm IOP assessment) - *If a lens is damaged during removal, a new lens cannot be inserted in the patient's eye. Patients can remain on the study if at least one LL-BMT1 lens is able to be reinserted.*
- IOP (measured at 4 pm  $\pm$ 1 hour)
- LL-BMT1 reinsertion (directly after 4 pm IOP assessment)

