#### **Day 4 (Visit 7): On-treatment assessment**

- Concomitant medications
- AEs
- Heart rate and blood pressure
- BCVA
- Biomicroscopy
- LL-BMT1 removal (directly before 8 am IOP assessment) - *If a lens is damaged during removal, a new lens cannot be inserted in the patient's eye. Patients can remain on the study if at least one LL-BMT1 lens is able to be reinserted.*
- IOP (measured at 8 am  $\pm$ 1 hour)
- LL-BMT1 reinsertion (directly after 8 am IOP assessment)

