### 8.2 SAFETY AND OTHER ASSESSMENTS

Abnormal findings that are of clinical significance will be recorded as AEs on the eCRFs.

- **Ultrasound pachymetry.** Corneal thickness will be measured using an ultrasound pachymeter.
- **Humphrey visual field assessment.** Visual field (perimetry) will be assessed using a Humphrey Field Analyzer. If Humphrey visual field assessment has been completed within 6 months of Screening Visit, it does not have to be repeated at the Screening Visit
- **Contact Lens (CL) Assessment:** Assessments will include contact lens centration, movement with blinking, and lens surface wettability/deposits, as described in ISO 11980:2012.
- **Heart rate and blood pressure.** Heart rate and blood pressure will be measured by a manual or automated sphygmomanometer.
- **Pregnancy testing.** Pregnancy testing will be performed using a human chorionic gonadotropin pregnancy urine dipstick test on women of childbearing potential.
- **Best-corrected visual acuity.** BCVA will be quantified using the ETDRS visual acuity protocol (at a distance of 3 m) and the number of letters read correctly will be recorded on the eCRF.
- **Biomicroscopy.** Biomicroscopy will be performed by slit-lamp examination of conjunctiva, cornea, and iris with findings reported on a scale of 0 = none, 0.5 = trace, 1 = mild, 2 = moderate, and 3 = severe. The status of the lens will be assessed using the Age-Related Eye Disease Study scale.
- **Goldmann applanation tonometry.** IOP will be measured with a Goldmann applanation tonometer. During the study, the LL-BMT1 contact lens will be removed in order to perform IOP assessment. Of particular significance, all lens insertions and removals will be conducted by the investigator. IOP will be assessed 3 minutes after lens removal, with the goal of reinserting the lens within 5 minutes of removal. Two consecutive IOP measurements of each eye were obtained. If the 2 measurements differed by more than 2 mmHg, a third measurement was obtained. For each eye, IOP was analyzed as the mean

of 2 measurements or as the median of 3 measurements. For each patient, change from baseline IOP was determined by averaging the values for each eye (Sherwood 2006).

- **Conjunctival hyperemia.** The Efron Grading Scales for Contact Lens Complications will be performed using a conjunctival hyperemia scale.

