5.2 Secondary Endpoints

The secondary safety endpoints include the following:

- AEs
- Concomitant medications
- Heart rate and blood pressure
- BCVA
- IOP
- Biomicroscopy
- Conjunctival hyperemia
- Percent of patients with ≥ 5 mmHg increase from baseline in IOP at each visit
- Abnormal slit-lamp biomicroscopy findings at the Baseline, Day 1, and Day 7 Visits
- Contact lens protein deposits at the Day 7 Visit
- Change from Baseline in CLDEQ-8 results at the Day 7 Visit

The secondary efficacy endpoint will be the change from baseline in IOP at each visit.

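### The slit-lamp endpoint tabulates status at three visits, with no cut-off for *Abnormal*, instead of worsening from each eye's pre-insertion grade, and it omits the Day 4 exam

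*SAP*

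**What the plan says.** Protocol 8.2 describes a graded exam of conjunctiva, cornea and iris, with "findings reported on a scale of 0 = none, 0.5 = trace, 1 = mild, 2 = moderate, and 3 = severe". The crystalline lens is assessed separately, on a named scale whose levels the protocol does not list.

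The endpoint does not use those grades directly. SAP 5.2 lists "Abnormal slit-lamp biomicroscopy findings at the Baseline, Day 1, and Day 7 Visits", and Protocol 9.4.2 defines the endpoint in the same way. SAP 6.8 adds a second label, "Abnormal” and “Severe” slit-lamp biomicroscopy findings", at the same three visits. No section says which grade makes a finding abnormal, and none gives a change, shift or worsening rule. In the same SAP 6.8 list, the questionnaire endpoint is "Change from Baseline in CLDEQ-8 results at the Day 7 Visit", and the IOP safety endpoint is an increase of at least 5 mmHg from baseline.

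On timing, the Day 1 entry in Protocol 1.2 says of biomicroscopy that the "procedure should be performed before study intervention". Biomicroscopy is also scheduled at the visit headed "Day 4 (Visit 7): On-treatment assessment" and in the Day 4 column of Protocol 1.3, but Day 4 is not among the endpoint's visits.

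**The concern.** The study has a single arm, and safety is its primary objective. Without a control group, the only contrast available for a slit-lamp finding is the same eye before and after LL-BMT1 insertion. An endpoint that reports status by visit does not make that contrast.

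Eyes reach Day 1 after two weeks of nonmedicated lens wear. The eligibility criteria exclude adverse reactions to those lenses, clinically significant dry eye and contraindicating corneal pathology, but they do not exclude trace or mild grades. In an eye that starts with such a grade, a Day 7 label of *Abnormal* does not say whether the finding was already there, improved or got worse. Because the label has no cut-off, the meaning of the count is also left to be settled once the data are in hand.

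**Working it through.** The documents give no figure for this endpoint, so there is none to reproduce. The check asks how much of the recorded scale the labels preserve.

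**Inputs**
- Five ordered grades: 0, 0.5, 1, 2, 3 (Protocol 8.2).
- Labels: *Abnormal* and *Severe* (SAP 6.8); *Abnormal* alone (SAP 5.2, Protocol 9.4.2).
- *Severe* is taken as grade 3, which is the scale's own word.
- *Abnormal* has no stated cut-off, so three are assumed: above 0, 1 or more, 2 or more.

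**Step 1: possible worsening moves.** A move goes from a lower to a higher grade: C(5,2) = 10.

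**Step 2: moves that leave the label unchanged.** If the grades fall into groups of size n₁, n₂, … that share a label, the hidden moves number Σ C(nₖ,2).

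With both labels (groups: not abnormal / abnormal but not severe / severe):

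| Cut-off for *Abnormal* | Group sizes | Hidden moves | Which |
|---|---|---|---|
| above 0 | 1, 3, 1 | 0 + 3 + 0 = 3 of 10 | 0.5→1, 0.5→2, 1→2 |
| 1 or more | 2, 2, 1 | 1 + 1 + 0 = 2 of 10 | 0→0.5, 1→2 |
| 2 or more | 3, 1, 1 | 3 + 0 + 0 = 3 of 10 | 0→0.5, 0→1, 0.5→1 |

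With *Abnormal* alone (groups: not abnormal / abnormal):

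| Cut-off | Group sizes | Hidden moves |
|---|---|---|
| above 0 | 1, 4 | 0 + 6 = 6 of 10 |
| 1 or more | 2, 3 | 1 + 3 = 4 of 10 |
| 2 or more | 3, 2 | 3 + 1 = 4 of 10 |

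**Step 3: stable grades counted on Day 7.** An eye whose grade does not change is labelled abnormal on Day 7 for 4 of 5 grades (above 0), 3 of 5 (1 or more) or 2 of 5 (2 or more).

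**Step 4: visits.** Of the three endpoint visits, Baseline (Day 0) and Day 1 come before insertion. That leaves 3 − 2 = 1 on-treatment visit, Day 7. Protocol 1.3 schedules on-treatment biomicroscopy on two days, Day 4 and Day 7, so the endpoint uses one of the two.

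**Step 5: the alternative rule.** A rule based on an increase from the pre-insertion grade registers 10 of 10 worsening moves and 0 of 5 stable grades.

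**The case against.** The strongest reply is that this list item is not the whole slit-lamp analysis. SAP 5.2 also names biomicroscopy as a safety endpoint in its own right, and SAP section 6 summarises safety endpoints descriptively. Protocol 9.4.7 promises listings for each patient, and with 5 patients (10 treated eyes) a reader can follow every eye. Protocol 9.4.1 allows exploratory within-eye comparisons for quantitative variables. Clinically significant findings become AEs under Protocol 8.2. The endpoint is secondary and descriptive, with no hypothesis test.

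Most of this stands. A reader might infer that real worsening would go unseen in the study; the documents do not support that, because the grades are recorded and can be listed. A reader might also infer that stable old findings count as events. They do not: no section calls these findings events, the same findings appear at Baseline beside Day 7, and conditions present at screening are medical history under Protocol 8.3.4. Nor can it be said that *Severe* is missing from the crystalline-lens scale, since its levels are not given.

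The reply still does not supply the missing rule:
- Visit summaries are not paired. If one eye goes from 0.5 to 1 and another from 1 to 0.5, the two summaries are identical.
- Protocol 9.4.1 does not name slit-lamp grades, and the SAP does not repeat its within-eye comparison.
- Listings leave it to the reader to decide afterwards what counts as worsening.
- The AE route depends on a judgement of clinical significance in an open-label study. SAP 6.7 also defines treatment-emergent AEs by onset date, without the sentence on worsening of pre-existing events in Protocol 8.3.1.

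**Conclusion.** The point holds as a weakness of the pre-specified endpoint tabulation. The endpoint reports status at three visits, only one of them on treatment, with a label that has no cut-off. Under each of the three cut-offs tried, 2 to 3 of 10 possible worsening moves leave the SAP 6.8 labels unchanged (4 to 6 of 10 with the single label of SAP 5.2), and a stable abnormal grade is counted again on Day 7.

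This rests on reading *Severe* as grade 3 and *Abnormal* as a cut-off on the same scale. If *Abnormal* is instead the examiner's overall call, these counts do not apply, but the endpoint still has no within-eye comparison. The shares give every possible move equal weight. A reader might take them as the proportion of worsening eyes that would be missed; the documents give no grade frequencies from which that could be estimated.

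No sample size, error rate or primary endpoint is affected. It is a cheap improvement that is worth making because within-eye change is the only contrast this design offers.

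**What to change.** In SAP 5.2 and 6.8:
- Add a shift table per eye and per structure (conjunctiva, cornea, iris) from the Day 1 pre-insertion grade, or the Day 0 grade if Day 1 is missing, to Day 4 and to Day 7.
- Show any increase in grade, with grade 2 or more and grade 3 as separate rows.
- Report crystalline-lens status as change on its own scale.
- Tie *Abnormal* to a stated grade or drop it, and use the same labels in both sections.

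The cost is SAP wording and one extra table from exams already scheduled. The downside is that one-level steps such as 0 to 0.5 will include some grading noise; the separate rows for the higher grades let the reader see how much of any increase is of that kind.

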7 INTERIM ANALYSIS

No interim analysis is planned for this study.

8 VERSION HISTORY LOG

Version	Date	Implemented Changes	Author
1.0	11-FEB-2021	First Approved Version	[name]
